clomiphene citrate alone, metformin achieved a significantly higher ovulation rate than clomiphene citrate alone (20). These women were only followed for 35 days on metformin, but achieved a 35% ovulation rate in this period (20). Studies which systematically examined menstrual regularity in PCOS women on metformin over a longer period of time have noted substantial improvement. Regular cycles, suggestive of monthly ovulation, have ranged from 69-96%(17;21;22). Few studies have addressed the issue of pregnancy in PCOS women on metformin and these have been observational and limited by a small sample size. (17;23) A more complete discussion of these trials is found in discussion of the power analysis below under IV B. Sample Size.

The preliminary evidence suggests that metformin in PCOS women is well tolerated, results in spontaneous ovulation, and is without known adverse effects during early pregnancy. Recently a new sustained release form of metformin, metformin XR with brand name Glucophage XR, has become available, and while similarly efficacious in the treatment of type II diabetes as metformin, it has a more favorable side effect profile. There are no published reports of the efficacy and tolerability of metformin XR in women with PCOS.

III. Objectives

A. Primary Research Hypotheses

The primary hypothesis is that improving insulin sensitivity and inappropriate gonadotropin secretion in infertile women with polycystic ovary syndrome (PCOS) with metformin and clomiphene citrate is more likely to result in a live birth than treatment with Metformin alone or clomiphene alone.

NICHD Reproductive Medicine Network
PPCOS-Pregnancy in Polycystic Ovary Syndrome Protocol
Primary Outcome Measure

The primary outcome measure is the presence/absence of a live birth during the study period. The primary analysis of live birth rate within the three treatment conditions will employ an intent-to-treat approach. Hence, patients will be analyzed according to the treatment group to which they are assigned, even if they did not receive the intended treatment or received only a portion of it.

B. Safety Hypothesis

The hypothesis is that adverse event rates between regimens will be comparable.

Safety Measures

Safety measures will be the number and category of reported adverse events

C. Secondary Research Hypotheses

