1. Age, body mass index, testosterone, insulin, glucose, and proinsulin levels will be significant predictors of ovulation and conception regardless of treatment.
2. Improvement in body mass index, testosterone, insulin, glucose, and proinsulin levels will be significant predictors of ovulation and conception regardless of treatment.
3. Treatment with metformin XR in combination with clomiphene citrate is more likely to result in singleton pregnancy compared to treatment with Metformin XR alone or clomiphene citrate alone. Singleton pregnancy is defined as presence of an intrauterine gestational SAC with a fetal pole and observable heart motion.
4. Treatment with metformin XR alone or in combination with clomiphene citrate will less likely lead to a first trimester intrauterine fetal demise than treatment with clomiphene citrate alone.

NICHD Reproductive Medicine Network
PPCOS-Pregnancy in Polycystic Ovary Syndrome Protocol

5. Treatment with metformin XR alone is more likely to result in ovulation (increased ovulation rate) compared to treatment with clomiphene citrate. Treatment with both is most likely to result in ovulation.
6. The shortest time to pregnancy will be with metformin XR/clomiphene citrate, followed by metformin XR, followed by clomiphene citrate.

D. Planned / Supplemental Analyses

A set of supplemental analyses/sensitivity analyses, will be conducted to evaluate the effect of treatments by excluding randomized patients who were later discovered to be not eligible, or by excluding patients who did not adhere to the assigned drug regimen.

[figure not shown]
IV. Study Design

A. Overview

The study will be a multicenter, double blind, randomized trial designed to determine the most effective method of achieving a live birth in infertile PCOS women. Patients will be randomized to one of three treatment strategies: 1) metformin XR alone, 2) clomiphene citrate alone, or 3) combined metformin XR and clomiphene citrate.

A1. Schematic of the study design: (see following page)

NICHD Reproductive Medicine Network
 PPCOS-Pregnancy in Polycystic Ovary Syndrome Protocol

NICHD Reproductive Medicine Network
PPCOS-Pregnancy in Polycystic Ovary Syndrome Protocol

A.2 Study Population

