The following table summarizes the literature comparing combination metformin and clomiphene to either metformin alone, or clomiphene, either from randomized trials or series where the second drug was added if there were no response to the first. A sixth study by Ng et al, (26) enrolled 20 subjects, but reported only median ovulation rates per subject, which were not translatable into cumulative rates.

STUDY	SUBJECTS	# of Cycles	Outcome	Results
Randomized trials				
Nestler et al, 1998 (20)	Metformin alone: n=21 Metformin + CC: n=25 (Unselected)	2	Ovulation	Metformin alone: Cycle 1: 8%, Cycle 2: 8% Metformin + CC: Cycle 1: 48%, Cycle 2: 81%
Kocak et al, 2002, (27)	CC alone: n=28 Metformin + CC: n=28 (All clomiphene resistant)	1	Pregnancy	CC alone: 0% (note: upper bound of 95% CI= 10%) Metformin + CC: 11%
Vandermolen et al, 2001 (23)	CC alone: n=12 Metformin + CC: n=15 (All clomiphene resistant)	6	Pregnancy	CC alone: 7% Metformin+CC: 55%
Nonrandomized				
Batukan Arch Gynecol Obstet 2001 (28)	CC alone: n=24 (3 cycles), followed by Metformin + CC: n=23 (Unselected)	6	Pregnancy	CC alone: 4% Metformin+CC: 65%
Parsanezhad et al Int J Gynecol Obstet 2001; (29)	Metformin alone: n=33 (2 months), followed by Metformin + CC: n=32 (All clomiphene resistant)	3	Pregnancy	CC alone: 3.1% (2 months) Metformin/CC: 25% (3 months)

None of the studies provide data directly applicable to the primary outcome of this protocol, live birth rate after 30 weeks, or 6 cycles, of treatment.

NICHD Reproductive Medicine Network
PPCOS-Pregnancy in Polycystic Ovary Syndrome Protocol
A Markov state-transition model was constructed using the software program

DATA 4.0 (TreeAge Software, Williamstown, MA) to convert published ovulation or pregnancy rates from individual studies into estimates of live birth rates after 6 months of therapy. Relevant states for the model are Not Pregnant, Pregnant, Pregnancy Loss, and Live Birth. Since other potential causes of subfertility are ruled out by the protocol's inclusion/exclusion criteria, we assumed a relatively high conception rate of 35% for cycles where ovulation occurs. We assumed that 25% of all conceptions would result in a pregnancy loss, and that rates would not differ between treatment arms. Observed rates were converted to probabilities using the formula:

$$\text{Probability} = 1 - e^{-\text{rate} \cdot \text{time}}$$

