Conception will be confirmed, if suspected, by measurement of serum hCG. A urinary hCG may be sent as an initial screen. Conceptions will be followed by the serial rise of serum hCG and when a threshold level is obtained (2,000-4,000 mIU/mL), ultrasound will be utilized to determine location of the conception and number of implantation sites. Patients who conceive will be followed at the site until the pregnancy has advanced to the point of determining the number of gestational sacs, their location, and fetal viability as determined by visualization of fetal heart motion by ultrasonography. A conception with fetal heart beat is defined as pregnancy. At this point, approximately 6-8 weeks after conception, women will be referred to their prior or referring practitioner, or to an appropriate health care provider. Patients will be reminded to continue their prenatal vitamin or Folic Acid during pregnancy and provided with counseling about prenatal care. Women will be followed throughout pregnancy to determine the abortion rate and through delivery to determine pregnancy outcome. Patients will be informed to notify study personnel of the outcome of the pregnancy. Phone contacts will be initiated if the patient has not contacted study personnel by six weeks beyond the original estimated

NICHD Reproductive Medicine Network
 PPCOS-Pregnancy in Polycystic Ovary Syndrome Protocol

date of confinement. Delivery records will be requested to determine the birth weight, length of gestation, and any perinatal complications of mother or infant. If delivery records are not available, patient self-report will be acceptable, however, every effort will be made to obtain records.

Unblinding of Medication Assignments:

Study medication assignments will not be routinely unblinded until the results of the study have been released. Emergency unblinding will be at the discretion of the site P.I.

Timeline for Proposed Protocol

The timeline below is a conservative estimate of the time needed to complete the trial, analyze the data, and achieve publication of the primary publication summarizing the results of the trial. The study should be completed, including pregnancy outcome in all randomized women by year four and data analysis complete by the end of that year.

Preparation and submission of the first article should be achieved by the fifth year of the grant.

	Year 1	Year 2	Year 3	Year 4	Year 5
Protocol Completion					
Subject Recruitment					

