The completed case report forms (CRF) will follow these guidelines: All data on the CRFs will be entered in ink. No data entry in the original CRF may be deleted or corrected by erasure, use of ink eradication fluid or any other such means. When a data entry is in error, draw a single line through the erroneous entry (the original data must remain discernible) and indicate the correct data in whatever way is appropriate. These changes should be initialed by the P.I. or designated study coordinator. Validity of data

NICHD Reproductive Medicine Network
PPCOS-Pregnancy in Polycystic Ovary Syndrome Protocol
recorded on CRFs during each patient visit will be attested to by one of the investigators
by a dated signature on an appropriate CRF page. All questions should be answered.
Data management will be as per DCC guidelines.

R. Competency to perform procedure/tests in the protocol

The principal investigator will be responsible for ensuring that laboratory and patient tests performed as part of the study are performed by competent personnel. These tests include semen analysis, ultrasonography of the pelvis, sonohysterography and/or hysterosalpingography of the uterus and fallopian tubes. The criteria for determination of competency may vary between sites in the study.

V. DATA ANALYSIS

All statistical tests will test non-directional hypotheses. The level of significance will be set at 0.05 for primary analyses and 0.05 for secondary analysis. An intent-to-treat principle will be employed during the primary analysis of the primary efficacy and safety measures. For the intent-to-treat analyses, randomized women will be included regardless of whether or not the patient received the assigned treatment, the patient was compliant with the treatment plan, and/or the treatment was administered according to randomization assignment.

A. Primary Efficacy Measure

Primary Analysis: A live birth will be defined as delivery of any viable infant. The primary analysis of the primary endpoint will include the following procedures. A chi-square test for equal proportions will be performed to evaluate whether live birth rate in Metformin/clomiphene group is the same as one in the group of either Metformin alone or clomiphene alone that has the higher live birth rate. If the test is not significant, a standard chi-square test will be used to examine differences in proportions in live births

NICHD Reproductive Medicine Network

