- An ovulation will be defined as an elevated weekly progesterone level separated by at least one week with a nonovulatory progesterone level. A binary variable indication whether the patient ovulated or not will be created for each cycle. Furthermore, cycles to first ovulation will be used as time to event variable.
- Time to pregnancy is defined as the number of cycles required to achieve a viable implantation (detection of fetal heart beat). Weeks from pregnancy to live birth will also be used as a time to event variable for patients who did not have miscarriages.
- Conception. Conception is confirmed by a positive serum hCG value. Cycles to first conception will be used as a time to event variable.

E. Drop outs/Treatment Failures

Dropouts, either by patient choice or physician recommendation due to adverse effects or poor compliance will be analyzed by intention to treat as treatment failures. Subjects who have completed 30 weeks or 6 treatment cycles without a pregnancy will also be considered as treatment failures. Subjects who conceive and are lost to follow up will be considered as a treatment success. It is considered unlikely that the patients will be lost to follow-up after a conception on a treatment regimen.

NICHD Reproductive Medicine Network
PPCOS-Pregnancy in Polycystic Ovary Syndrome Protocol

F. Interim Analysis

Analysis Plan: An interim analysis will be conducted on the primary endpoint when 50% of the study participants have completed treatment. The primary analysis described above will be performed and the O'Brien-Fleming (1979) method will be applied to adjust for at the number of looks at the primary endpoint. The interim analysis should also provide a detailed summary of adverse events reported. The critical value for the primary analysis will be specified in the detailed analysis plan. The results of the interim analysis will be submitted to the Data Safety and Monitoring Committee (DSMC). The interim analysis results will be presented in a blinded fashion to the DSMC, who will then evaluate the findings to determine whether the trial should be continued, modified, or discontinued.

Stopping Rules: The stopping rule for the O'Brien-Fleming method compares the statistic Z_i with $Z^*(N/i)^{.5}$, where Z^* is the critical value for the significance level (.05), N is the total number of analyses ($N = 2$) and i is the analysis number (for the one planned analysis, $i = 1$).

VI. DISCLOSURE OF DATA

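### Women who conceive and are then lost to follow-up score as successes on a live-birth endpoint: a should-fix contradiction, with a small effect if such losses are rare

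*Protocol*

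**What the plan says.** - Section III.A sets the endpoint: "The primary outcome measure is the presence/absence of a live birth during the study period". Section V.A defines the event: "A live birth will be defined as delivery of any viable infant".
- Section V.E scores dropouts, by choice or on medical advice, as treatment failures. It does the same for women who finish treatment without a pregnancy. It then adds: "Subjects who conceive and are lost to follow up will be considered as a treatment success". It calls such loss unlikely and gives no figure.
- Two stages are kept apart. Section V.C: "Conception is confirmed by a positive serum hCG value". Section IV.F, Pregnancy Visits: "A conception with fetal heart beat is defined as pregnancy".
- The planning model in section IV.B.1 states: "We assumed that 25% of all conceptions would result in a pregnancy loss, and that rates would not differ between treatment arms".
- Secondary hypothesis 4 (section III.C) expects the loss rate to differ: metformin XR, alone or combined, "will less likely lead to a first trimester intrauterine fetal demise than treatment with clomiphene citrate alone".
- Section IV.F describes outcome tracing. Women are followed at the site until fetal heart motion is seen and then referred out. A telephone contact follows if nothing has been heard by six weeks after the due date. Delivery records are sought, and self-report is accepted if there are none.

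**The concern.** Section V.E sets the intention-to-treat scoring and live birth is the only primary endpoint, so a success there can only mean a live birth. A positive hCG with no known outcome is then recorded as a delivered infant. This does not fit the definition in section V.A. It also implies no pregnancy loss among women whose outcome is unknown, against the 25% assumed in section IV.B.1.

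The scoring sentences overlap as well. A woman who conceives and then withdraws by choice is a failure under one sentence and, once contact is lost, a success under another. A woman lost with only a positive hCG has had no pregnancy as section IV.F defines it, so she too can fit both.

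At stake is misclassification of the primary endpoint, in numbers that can differ by arm. The supplemental analyses in section V.A exclude ineligible or non-adherent women and do not test this rule.

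**Working it through.** **Inputs from the protocol.** Planned live-birth rates are 45% (combination), 30% (metformin) and 25% (clomiphene). The design uses two-sided alpha 0.025, 80% power and 226 women per arm (section IV.B.5). Loss is 25% of conceptions in every arm (section IV.B.1).

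**Assumed input.** f is the share of conceivers lost to follow-up. The protocol gives no value, so 5%, 10% and 20% are shown, equal across arms.

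**Step 1: the plan's own figure.** For 45% against 30%, pooled variance, no continuity correction:

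n = [2.2414 × √(2 × 0.375 × 0.625) + 0.8416 × √(0.45 × 0.55 + 0.30 × 0.70)]² / 0.15² = 196.7, so 197 per arm, as stated. 197 × 1.15 = 226.55, stated as 226. Power at 226 per arm is 85.7%.

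**Step 2: implied conception rates.** c = live-birth rate / 0.75.
- Combination: 0.45/0.75 = 60%, about 136 of 226 women.
- Metformin: 0.30/0.75 = 40%, about 90 women.
- Clomiphene: 0.25/0.75 = 33.3%, about 75 women.

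**Step 3: the rule as written.** Credited rate = c × (0.75 + 0.25f), so the excess in an arm is 0.25 × f × c. At f = 10%: combination 0.60 × 0.775 = 46.5%, metformin 0.40 × 0.775 = 31.0%, difference 15.5 points.

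**Step 4: documented live births only.** Credited rate = c × 0.75 × (1 − f). At f = 10%: 40.5% and 27.0%, difference 13.5 points.

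| f | False live births under the rule (combination / metformin / clomiphene) | Combination minus metformin, rule as written | Same, documented only | Power, rule as written | Power, documented only |
|---|---|---|---|---|---|
| 0% | 0 / 0 / 0 | 15.0 | 15.0 | 85.7% | 85.7% |
| 5% | 1.7 / 1.1 / 0.9 | 15.25 | 14.25 | 86.7% | 82.4% |
| 10% | 3.4 / 2.3 / 1.9 | 15.5 | 13.5 | 87.6% | 78.9% |
| 20% | 6.8 / 4.5 / 3.8 | 16.0 | 12.0 | 89.4% | 70.8% |

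Crediting each lost conceiver at 75% returns 15.0 points at every f.

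**Step 5: what drives the direction.** In general the excess in an arm is conceptions × loss rate × share lost to follow-up.
- Equal live births (30%), equal loss (25%) and equal f: both arms gain the same amount and the test keeps its level.
- Equal live births (30%), loss 25% against 35% (assumed): conception rates are 40.0% and 46.2%. The second arm gains 0.3 to 0.9 points for f = 5% to 15%, and rejection at nominal 0.05 rises to between 0.051 and 0.055.
- Combination against clomiphene with assumed losses of 15% and 25% and f = 10%: the excess is 0.45/0.85 × 0.15 × 0.10 = 0.79 points for combination and 0.25/0.75 × 0.25 × 0.10 = 0.83 points for clomiphene. The arm with fewer conceptions gains slightly more.

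**The case against.** **The effect is small.** Section V.A compares combination with the better single agent, which is metformin under the planned rates. The inflation there is 0.25 to 0.5 points for f = 5% to 10%, against a planned 15. Follow-up is also active: site visits until heart motion, release forms for the prenatal caregiver and delivery hospital, telephone contact, records and self-report. This stands, and it limits the severity.

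**The strict alternative errs more under the planned rates.** If 75% of conceptions end in live birth, calling a lost conceiver a success is wrong 25% of the time and calling her a failure is wrong 75% of the time. At f = 10% about 14 combination conceivers are lost; the present rule misclassifies about 3 and the strict rule about 10. The order reverses only if more than 50% of the lost women miscarried. This also stands. It is why the strict rule needs a bracket, but it does not reconcile the present rule with the endpoint definition.

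**Stronger readings that a reader might infer.**
- That the rule always favours the arm with more conceptions. This needs equal loss rates and equal follow-up; the last case of step 5 shows otherwise.
- That it manufactures a treatment effect. It does not when true live-birth rates, loss rates and follow-up are equal.
- That the lost women are mainly hCG-only conceptions. If all of them had miscarried, with overall loss still 25%, the difference would be 16.0 points at f = 5% and 17.0 at f = 10%. Nothing in the protocol supports that; women lost after referral would already have a documented heart beat.
- That live birth was chosen over conception because losses may differ by arm. The protocol does not give this reason.

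**Sensitivity analyses belong in the SAP.** Their detail may. The scoring rule itself is fixed in the protocol, so it is a stated choice and not missing detail.

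**Conclusion.** The contradiction holds on the text: an endpoint defined as delivery of a viable infant is scored as met on a positive hCG with unknown outcome. The rule credits 100% where the protocol's model gives 75%, and its scoring sentences overlap.

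With the planned rates, 25% loss in every arm and equal follow-up, it inflates combination minus metformin by about 0.25 points at 5% lost and 0.5 points at 10%. The shares lost are assumptions. The direction is conditional on loss rates and follow-up being similar by arm. Secondary hypothesis 4 bears mainly on contrasts with clomiphene alone, since both metformin arms are expected to lose fewer pregnancies.

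This is a should-fix point. The case for change rests on misclassification of the primary endpoint. The numerical effect is small if loss after conception is as rare as the protocol expects.

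**What to change.** In section V.E, replace the success sentence with one rule for all randomised women: in the primary analysis only a documented live birth counts, from delivery records or self-report (both already accepted in section IV.F). A woman without one is not a live birth, whether or not she conceived. This also removes the overlap between the scoring sentences.

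Bracket it with sensitivity analyses, whose detail can sit in the SAP:

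1. The present success rule, and that rule restricted to women with a documented fetal heart beat.
2. Imputation by last pregnancy stage reached, or a 75% credit for each lost conceiver.

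Report the number of conceivers lost to follow-up by arm and by stage, so that a reader can see how much rests on the rule.

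The cost is one sentence and a few extra runs. The downside should be stated: under the planned rates the new primary rule is conservative. It gives 14.25 points at 5% lost, and 13.5 points with about 79% power at 10% lost, against 15.0 points and 85.7% with complete follow-up.

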Ideally, the threshold for identifying a minimum difference between treatments is informed by prior data on a variety of factors important for decision making, including efficacy in randomized trials, effectiveness in clinical practice, side effects, patient values for benefits, side effects, and risks of each treatment, health-related quality of life, and costs. Unfortunately, data that would allow estimation of these factors for the clinical situation addressed by this protocol are unavailable.

In the absence of specific data, we assume that any combination of two or more drugs must be superior to either agent alone in order for the combination to be considered the "best" treatment. In other words, given that combination therapy inevitably will cost more than either agent alone, that it will carry the risks of the side effects of both agents, and be less convenient for patients than either alone, the combination of metformin plus clomiphene citrate must be superior to either agent alone by some amount in order for it to become the treatment of choice.

We propose that an absolute difference in live birth rates after 6 months of therapy of **15%** is clinically important.

3. Null Hypotheses

NICHD Reproductive Medicine Network
PPCOS-Pregnancy in Polycystic Ovary Syndrome Protocol

(A) The live birth rate after 30 weeks of therapy with the combination of metformin plus clomiphene citrate is not different from the live birth rate after either metformin alone or clomiphene alone.

(B) The live birth rate after 30 weeks of therapy with metformin alone is not different from the live birth rate after clomiphene alone.

4. Possible Study Outcomes and Interpretation:

a) Null hypothesis (A) is rejected

If the null hypothesis is rejected, we expect that combination therapy is superior to either agent alone, and, barring significant differences in adverse events, combination therapy becomes the treatment of choice.

b) Null hypothesis (A) is accepted, but null hypothesis (B) is rejected

If the difference between combination therapy and one of the single agents is less than 15%, then null hypothesis (A) is accepted. If the observed difference between the single agents is greater than 15%, we expect that metformin would become the treatment of choice, barring substantial differences in adverse events. (This also allows for the possibility that Metformin alone will be at least 15% more effective than clomiphene alone).

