.50	.35	206/arm	237/arm	711
.45	.30	197/arm	226/arm	678
.40	.25	185/arm	213/arm	639
.35	.20	168/arm	193/arm	579

Based on these results, it is concluded that a study with 226 patients/arm is adequately powered to detect an absolute difference of 15% in live birth rates between two treatment arms, given the best estimates of success rates from the available literature.

A continuity correction was not applied to the sample size estimates for the chi-square test statistic. Such a correction is not necessary due to the expected size within each cell (32).

NICHD Reproductive Medicine Network
 PPCOS-Pregnancy in Polycystic Ovary Syndrome Protocol

6. Total Sample Size

The study will include 678 patients (226 per treatment arm).

C. Allocation of Intervention

1. Timing

A timeline is provided below:

Figure 1: Study Overview

Time line (~weeks)	-4 to 0	1	1-30	~~30-70
Study Phase	Consent PCOS Screen	Progestin withdrawal and Randomization		Pregnancy
Treatments	None- Complete infertility evaluation as necessary	Treatment Arm 1	Metformin XR	None-Collect pregnancy outcome data
		Treatment Arm 2	Clomiphene citrate	
		Treatment Arm 3	Metformin XR/Clomiphene citrate	
Visits	1 or more visits	2-30 (maximum weekly visits for 6 ovulatory cycles)		As necessary

2. Method

a. Randomization Scheme

Six hundred seventy-eight (678) women will be randomized to one of the three treatment conditions. Using a 1:1:1 treatment ratio, there will be 226 women assigned to each treatment arm. The scheme will be a stratified randomization with permuted blocking within each stratum. Stratification variables will be site and prior exposure to either

NICHD Reproductive Medicine Network
PPCOS-Pregnancy in Polycystic Ovary Syndrome Protocol
clomiphene citrate or metformin XR. The DCC statistician will generate the randomization scheme for the study. Because this is double-blind study, the randomization scheme (including block size) will not be disclosed to the RMN investigators or staff, including the Lead Investigators. Unless otherwise specified, treatment arm data will be presented in a blinded fashion within DSMB reports.

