A serious adverse event is one that is fatal or immediately life-threatening, severely or permanently disabling, requires or prolongs inpatient hospitalization, overdose (intentional or accidental), congenital anomaly, pregnancy loss after 12 weeks gestation or any event so deemed as serious by the P.I. at each RMN site. If any serious event occurs and is thought to be related to the study medication, the study medication will be discontinued. Twenty-four hour unblinding will be available through the IVRS system to break the randomization code for the individual patient if this is required by the P.I. for proper treatment of the patient.

J. Study Medication Related Adverse Events (*Please refer to Appendix E for details*)

There are a number of adverse events that are potentially related to study medication.

Metformin

Gastrointestinal symptoms (diarrhea, nausea, vomiting, abdominal bloating, flatulence, metallic taste in the mouth and anorexia) are the most common reactions to metformin XR and approximately 30% more frequent in women with metformin XR compared to placebo treated patients. These symptoms will be managed with a step down decrease in the daily metformin XR dose (one tablet per day per week) until symptoms resolve.

These symptoms alone will not be a reason for withdrawal from the study unless a patient is unable to tolerate any dose of the medication.

There is a small risk of lactic acidosis among women taking this medication. This most commonly occurs in patients with poorly controlled diabetes and impaired renal function. Women with these pre-existing medical problems will be excluded from the RMN Protocol

NICHD Reproductive Medicine Network
PPCOS-Pregnancy in Polycystic Ovary Syndrome Protocol

protocol as per the exclusion criteria. There have been reports of lactic acidosis induced by exposure to iodine-containing radiocontrast agents, such as those used for an intravenous pyelogram or even for hysterosalpingogram, if there is intravasation. Metformin XR will be stopped prior to procedures involving exposure to radiocontrast agents to reduce the chance of developing lactic acidosis (one week prior to medication and resume one week after the test). The development of lactic acidosis for any reason will be a reason for discontinuing the study.

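### Interim live-birth results go to the DSMC blinded, with no stated route to the arm codes, although the test it must act on is non-directional and defined by arm identity

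*Protocol*

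**What the plan says.** Section V.F plans one interim analysis of the primary endpoint, when half the participants have completed treatment: "The primary analysis described above will be performed and the O'Brien-Fleming (1979) method will be applied". On reporting it states: "The interim analysis results will be presented in a blinded fashion to the DSMC". The committee is then to "evaluate the findings to determine whether the trial should be continued, modified, or discontinued".

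Section V.A defines the primary analysis in two steps. Step 1 compares the combination with "either Metformin alone or clomiphene alone that has the higher live birth rate". Step 2 is conditional: "If the test is not significant, a standard chi-square test will be used to examine differences in proportions in live births" between the two single agents. The opening of section V makes all tests non-directional, and the stopping boundary in V.F carries no direction either.

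Three other places bear on this:

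- **IV.C.2.a** sets the general default, subject to anything specified elsewhere: "treatment arm data will be presented in a blinded fashion within DSMB reports".
- **V.B** also has adverse-event summaries presented blinded in each DSMB report, but lets them be unblinded on formal request. V.F has no such clause for efficacy.
- **IV.B.4** gives the two directions different consequences. If hypothesis (A) is rejected in favour of the combination, then "barring significant differences in adverse events, combination therapy becomes the treatment of choice". If the combination is below one of the single agents (Scenario 2), only the comparison of the single agents is considered meaningful.

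**The concern.** A monitoring committee needs the direction of an effect, and the drug it belongs to, before it recommends stopping or changing a trial. Here the rule for what it sees works against the test it is given. A two-sided crossing in a comparison of coded arms can mean that the combination is superior or that it is inferior, and IV.B.4 treats those results very differently. The same section makes preference for the combination depend on adverse events, so live births must be weighed against harms by drug, which coded efficacy results do not allow.

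This is not a detail left to a later document. V.F states the blinding outright and defers only the critical value to the detailed analysis plan. At stake is the soundness of the trial's one planned efficacy look.

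**Working it through.** **Inputs.** Total 678, randomised 1:1:1 (IV.B.6, IV.C.2.a). Interim at 50% (V.F). Design live-birth rates: combination 45%, metformin 30%, clomiphene 25% (IV.B.5). Boundary Z* × (N/i)^0.5 with N = 2 and i = 1 (V.F). V.F gives no number for Z*; 1.96 is assumed for the 0.05 level.

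- Interim size: 678 × 0.5 = 339, and 339 / 3 = 113 per arm, assuming an even split and known outcomes.
- Boundary: 1.96 × √2 = 2.772.

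**Step A. What coded arms reveal.** Call the coded arms X > Y > Z by observed live-birth rate. C is the combination, M metformin, L clomiphene. The six possible orderings give:

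| True order (X, Y, Z) | Step 1 pair | Step 2 pair |
|---|---|---|
| C, M, L | X–Y | Y–Z |
| C, L, M | X–Y | Y–Z |
| M, C, L | X–Y | X–Z |
| L, C, M | X–Y | X–Z |
| M, L, C | X–Z | X–Y |
| L, M, C | X–Z | X–Y |

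- *Step 1 crosses, so step 2 is not run.* A pair X–Y fits four orderings: the combination is the better arm in two and the worse arm in two. The chi-square statistic is symmetric and cannot separate them. A pair X–Z occurs only when the combination is last.
- *Step 1 does not cross, so step 2 is reported.* The three pairs of comparisons are all different. The combination is always the arm in step 1 that is absent from step 2.
- *In no row* do the tests show which single agent is metformin: M and L swap without changing the display.

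**Step B. How often each case arises.** With pooled proportion p̄, Z = (p_C − p_H) / √[2 p̄(1 − p̄)/113], where p_H is the higher single-agent rate. At 45% against 30%, p̄ = 0.375 and Z = 0.15 / √(2 × 0.375 × 0.625 / 113) = 0.15 / 0.0644 = 2.33. This is below 2.772, so a crossing needs an observed gap wider than planned. Summing the three binomial distributions exactly at 113 per arm gives:

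| True rates (C, M, L) | Step 1 crosses | Direction | Step 2 run |
|---|---|---|---|
| 45%, 30%, 25% (design) | 27.8% | all for benefit | 72.2% |
| 30%, 30%, 30% | 0.5% | nearly all against the combination | 99.5% |
| 30%, 45%, 25% (illustrative) | 32.7% | all against the combination | 67.3% |

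In the last row the 32.7% divides into 19.3 points with the combination strictly in the middle, 2.1 points with it tied for last, and 11.3 points with it strictly last. In the 19.3 points, the coded display has the same form as a benefit.

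**Step C. Effect of Scenario 2.** If the IV.B.4 restriction is applied, step 1 is run only when the combination ranks first. A crossing then has one meaning. A committee that knows the rule can also read off which code is the combination. V.A does not state the restriction: it calls for step 1 whatever the ordering.

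**The case against.** The strongest reply is that IV.B.4 settles the direction. Under Scenario 2 an inferior combination is never tested against the better single agent, so a significant first step can only be a benefit. That stands as a reading of IV.B.4, and the illustrative rates of 30% against 45% and 25% are not the protocol's. But V.A, which V.F applies at the interim, carries no such restriction. The two sections need reconciling before the reply can be relied on.

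Second, V.B lets the committee formally request unblinded adverse events, and IV.I has relevant safety information forwarded to the DSMB. This stands: a reader might infer that the committee cannot see harms by drug, and the documents do not support that. If one set of codes served the whole report, such a request would also reveal the efficacy arms. The protocol does not say that it would, and the V.B clause is written for adverse events only.

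Third, a reader might infer that the test itself unblinds the committee. It does so only in part. The combination is identified when step 2 is reported, or when it is last in step 1; the single agents are never told apart by the tests. Gastrointestinal symptoms, described in IV.J as "approximately 30% more frequent in women with metformin XR compared to placebo treated patients", may hint at the metformin arms, but that is a possibility, common to any drug with recognisable side effects.

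Fourth, coded reports are accepted practice and can restrain a committee's prior expectations, so it would be too strong to say that blinding the committee serves no purpose. They work when the codes can be obtained. A monitoring charter, not shown, may allow this, and nothing in V.F forbids a request. What remains is that V.F states blinding for the efficacy decision and offers no route out of it.

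**Conclusion.** The concern holds in a limited form. V.F fixes blinded efficacy results for a continue, modify or discontinue decision, gives no route to the codes, and rests that decision on a non-directional test defined by arm identity. As V.A is written, a first-step crossing between the two best arms leaves the direction for the combination unstated. That describes every one of the 27.8% of crossings at the design rates, to within rounding, and about 19 of 32.7 points in the illustrative inferior case. In the other 72.2% at the design rates, step 2 is reported and the combination's code is exposed anyway.

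This rests on three assumptions: blinding means coded arms (with pooled arms the test could not be shown at all), 113 women per arm with known outcomes, and Z* = 1.96. The display argument in Step A does not depend on the last two. The documents do not support a claim that the committee would in fact stop wrongly or miss a drug-specific harm: it is asked to evaluate findings, a crossing does not force a stop, and safety routes exist. The point is moderate and should be corrected.

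**What to change.** 1. In V.F, replace the blinding sentence with a rule that interim efficacy and safety results go to the DSMC in a closed report, either by identified arm or by coded arm with the codes released on the committee's request and in any case before it recommends stopping or modifying. State that investigators, site staff and operational staff stay blinded.
2. Make the matching exception in IV.C.2.a, and extend the formal-request clause of V.B to efficacy results.
3. Reconcile V.A and V.F with Scenario 2 of IV.B.4, so that the direction of a first-step crossing is stated.
4. Use one name for the committee: IV.C.2.a and V.B say DSMB, V.F says DSMC.

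The cost is wording and a closed-session report. The downside is that this report must be restricted to DSMC members and the reporting statistician. IV.C.2.a already has the DCC statistician generate the randomisation scheme, so no new unblinded role is needed if that person does the reporting. Sample size, endpoint and patient procedures do not change.
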